**FORM: Application for Human Research**

NUMBER	FORM DATE	PAGE
F200		8 of 18

3) Setting of the Human Research

The PI is an assistant professor in the Department of Orthopaedic Surgery and surgeon with the University of Arizona Health Network. Subjects will be recruited from the outpatient clinic of Drs. [name] (PI) and [name]. The age, gender, height, weight, activity level, pain level, and physical exam findings of patients will be obtained directly from the subject, the subject's medical record, or from direct examination and then recorded in a password protected excel file. The online survey can be completed from any computer available to the subject. Intense therapeutic ultrasound and diagnostic ultrasound will be administered in the Human Movements Biomechanics Lab (BRL B101).

4) Resources available to conduct the Human Research

Equipment for intense therapeutic ultrasound will be provided by [name] and [name] from Guided Therapy Systems. The equipment for measuring height and weight will be in the orthopedic clinic. Personnel available to conduct the study include 2 surgeons, 1 clinical research coordinator, 2 sonographers, 1 medical student, and 2 undergraduate assistants. These individuals will be available to recruit and consent patients, coordinate and conduct the study, analyze the data, and produce a manuscript.

5) Study Population

Male and female adults (18 years or older) with plantar heel pain and point tenderness near the medial calcaneal insertion of the plantar fascia for at least three months without improvement will be considered for inclusion into the study. Subjects with diabetes, bilateral plantar heel pain, current systemic or local infection, previous foot surgeries, other foot/ankle pathologies (inflammatory arthritis, gout, neurologic disorders, connective tissue disorders and malignancy), contraindications to the use of NSAIDs, and pregnancy will be excluded. The target enrollment of this pilot study is 50 participants.

6) Recruitment Methods and Consenting Process

Subjects will be recruited utilizing public media, list serves, community organizations, and via referral. Please see the attachments to this application for an electronic media and brochure representations of the advertisements to be utilized. We would like to select from the following wording to produce recruitment materials -

"We are seeking adults with chronic heel pain. Have you had chronic heel pain? Chronic heel pain is pain which has been present for at least 3 months and may be the result of plantar fasciitis. Have you had heel pain for the last 3 months? It may be the result of plantar fasciitis. Plantar Fasciitis is a painful, inflammatory condition occurring where the plantar fascia attaches to the calcaneus (heel bone). The most common symptoms are 1) pain with the first few steps in the morning, 2) pain at the beginning of an activity which improves as the plantar fascia is stretched during the activity, 3) pain and stiffness with prolonged standing, and 4) pain at the end of the day. The standard treatment of Chronic Plantar Fasciitis consists of stretching, anti-inflammatory medications (NSAIDS), and heel cups. Despite these treatments, 5% - 20% of patients will still have symptoms at 1 year! Participate in a study to determine the effectiveness of Intense Therapeutic Ultrasound for the treatment of Chronic Plantar Fasciitis. What is Intense Therapeutic Ultrasound? Intense Therapeutic Ultrasound (ITU) is a noninvasive method of healing tissues with sound waves. ITU promotes collagen generation and is FDA approved for the non-surgical lifting of the brow. What is the purpose of this study? The purpose of this study is to determine if intense ultrasound can promote healing of plantar fasciitis. This study will determine the effectiveness of ITU in speeding the healing of plantar fasciitis. The time required

**FORM: Application for Human Research**

NUMBER	FORM DATE	PAGE
F200		9 of 18

to heal will be compared for traditional treatment methods + placebo to that required by traditional treatment + ITU. Every subject will receive anti-inflammatory medication, a viscoelastic heel cup, and physical therapy. Patients receiving just these treatments will be compared to those also receiving ITU treatments. Who can participate? The following criteria are required for participation: A physician associated with the study has diagnosed you with plantar fasciitis. To be eligible you need to have chronic heel pain that is diagnosed as plantar fasciitis by a physician associated with the study. The/your symptoms exist in only one foot. You must not have diabetes or be pregnant. You must be 18 years or older. What will participation require? You will need to be assigned to either a control group (standard medical care) or to an experimental group (standard medical care + ITU). You will need to not use any other treatments. You will need to commit to the assigned treatment for 3 months. You will need to answer an additional online or telephone questionnaire at 6 months. Why should I participate? Although you will not receive payment, what is learned may benefit others! To participate, please call [contact information]. If interested, please call [contact information] or send an email to [contact information] and provide preferred contact information."

In addition to anatomical labeling of the *achilles tendon, calcaneus, and plantar fascia*, we would like to use the captions, "*Inflammation of the plantar fascia can cause heel pain*" and "*stretching the plantar fascia*."

Interested individuals who contact the laboratory will have the logistics of the study explained and be referred to the clinic for diagnosis and treatment of heel pain. All patients diagnosed with plantar fasciitis by participating physicians will be contacted by the research team to discuss the details associated with participation. We would like to obtain a temporary deferment of authorization to obtain contact information from the electronic medical record for those individuals who are initially identified in the clinics by participating physicians. Additionally, we would like permission to provide the consent and authorization forms and other information by e/mail should this be conducive to obtaining informed consent. The mailing is for informational purposes only to allow the subject more time to consider participation in the study. The informed consent process will be completed in person. Both English and Spanish versions of the consent forms will be utilized, although the Spanish consent form will be submitted as a modification once the English version is approved. Finally, we would like to provide a map and information sheet to assist participation in the study (see attachments).

7) Procedures involved in the Human Research

After obtaining informed consent and authorization from the subject, study personnel will verify the screening of participants utilizing the inclusion/exclusion criteria and collect the following information- age, gender, height, weight, activity level, pain level, and physical exam findings including x-rays - which will be recorded on the data abstraction sheet (see attachment). The activities strictly associated with the research are the assignment to a study group (Control or ITU), the administration of patient reported outcome measures (questionnaires), and therapeutic and/or diagnostic ultrasound (Table 1). Additionally, adverse events will be recorded at each visit (see attachment). Treatment tolerability will be prior to, immediately after, and at 2 days post-treatment.

Standard of care is integrated into both arms of the investigation and includes a structured physical examination, the use of an NSAIDs for 3 weeks (Naprosyn 500 mg po bid or Ibuprofen 800 mg po tid taken with meals), viscoelastic heel cups for 12 weeks, and supervised physical therapy with home exercise program for 6 weeks. These components are described below-

**FORM: Application for Human Research**

NUMBER	FORM DATE	PAGE
F200		10 of 18

Table 1. Calendar of Activities

Timeline	Standard of Care	Research Activity
-1	focused history, x-rays, NSAIDs, heel cups	Informed consent and assessment of inclusion/exclusion criteria; enrollment in the study (randomization to treatment group)
0	NSAIDs, heel cups, focused exam	questionnaires; ultrasound (diagnostic & treatment)
2 weeks	NSAIDs, heel cups, focused exam	questionnaires; ultrasound (diagnostic & treatment)
4 weeks	heel cups, focused exam	questionnaires ultrasound (diagnostic)
6 weeks	heel cups, focused exam	questionnaires ultrasound (diagnostic)
12 weeks	heel cups, focused exam	questionnaires ultrasound (diagnostic)
24 weeks		questionnaires

Structured physical examination. The focused exam will consist of assessment of hindfoot and midfoot alignment, inspection for swelling, palpation of the calcaneus and entire plantar fascia, range of motion of the ankle with the knee flexed and with the knee extended, and calcaneal squeeze test. Pertinent positive findings on exam include: valgus hindfoot, midfoot planus, tenderness to palpation at the insertion of the plantar fascia onto the calcaneus, ankle dorsiflexion less than 10 degrees with the knee extended or greater than 10 degree augmentation in ankle dorsiflexion with the knee flexed. Pertinent negative findings include: lack of swelling at the ankle and midfoot, no tenderness at the Achilles insertion, the retrocalcaneal bursae, along the arch, posterior to the medial malleolus, or at Baxters point, and positive calcaneal squeeze test.

Physical Therapy. Supervised physical therapy will occur two times per week and include gastrocnemius stretching, plantar fascia specific stretching, modalities (ice and heat), and plantar fascia deep tissue massage (see instructions to PT appendix 2 of the protocol). Use of advanced modalities such as iontophoresis, phonophoresis, or TENS will not be permitted. The home exercise program will consist of PF specific stretch and gastrocnemius stretch to be done for ten minutes two times per day (see home exercise program handout, Appendix 2 of the protocol). Subjects will be required to record the frequency of each exercise in a logbook (see Appendix 3 of the protocol).

The research components are described below-

Randomization and Blinding. Suitable subjects will be randomly assigned (1:1) to receive standard of care with a sham ultrasound treatment (Control group) or standard of care + ITU treatment (ITU group) by the application of an algorithm (e.g. even vs odd) to the number provided by a random-number generator. Most members of the research team and the subject will be blinded to group assignment. Only the clinical research coordinator and ultrasound treatment team will be privy to the subject's group assignment.

Patient Reported Outcome Measures (Aim 1). The principal aim of this study is to compare the efficacy of treatment and time course of response to treatment between the two groups using validated

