**FORM: Application for Human Research**

NUMBER	FORM DATE	PAGE
F200		7 of 18

fascia uniformly along with 68% of patients with CPF reporting central band tenderness as opposed to 26% having lateral band tenderness. In addition to the evidence of inflammation, the presence of a hyper-echoic lesion in the plantar fascia was noted in 68% to 84% of patients with CPF. Diagnostic ultrasound has also been used to quantify the effectiveness of treatments such as extra-corporeal shock wave therapy, NSAIDs and Botox injections for subjects with CPF.

More than twenty different treatments have been used for plantar fasciitis. The combination of rest, ice, stretching and NSAIDs are used as initial management in most patients and have been shown to effectively treat symptoms in 90% of patients in less than 12 months. However, 10% of patients fail conservative management and continue to have symptoms beyond 12 months (termed refractory plantar fasciitis or RPF). Surgery consisting of partial plantar fascia release or gastrocnemius recession is often considered in these patients. However, the outcomes of surgery are not uniformly positive with 50% of patients reporting residual symptoms. Moreover, evidence supporting surgical treatment of RPF is weak as there are no randomized controlled trials comparing its efficacy to other treatments. Thus, for many patients the risks of surgery such as arch instability, prolonged wound healing, and longer rehabilitation times simply outweigh the benefits. Is there a non-invasive treatment that can be used as an adjunct to speed healing in patients with CPF and as an alternative to surgery in those with RPF? The primary objective of this study is to evaluate the efficacy of combining the non-invasive treatment with intense therapeutic ultrasound (ITU) with standard care for the treatment of chronic plantar fasciitis. A secondary objective is to evaluate the tolerability and safety of intense therapeutic ultrasound in the treatment of plantar fasciitis.

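### Fifty subjects of widely varying symptom duration are allocated by simple, unstratified randomisation, with duration and prior treatment not among the listed baseline data, so a chance prognostic imbalance is neither limited nor, as listed, adjustable

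*Protocol*

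**What the plan says.** **Prognosis.** Protocol Section 3, 1) Background states that rest, ice, stretching and NSAIDs "have been shown to effectively treat symptoms in 90% of patients in less than 12 months", while "10% of patients fail conservative management and continue to have symptoms beyond 12 months"; the latter group is termed refractory (RPF). The recruitment text in 6) gives a different figure for persistence: "5% - 20% of patients will still have symptoms at 1 year". The background asks whether a non-invasive treatment could help as an adjunct in chronic disease and "as an alternative to surgery in those with RPF". The objective stated straight afterwards, and the three specific aims, concern chronic plantar fasciitis only.

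**Entry.** Under 5) Study Population, adults with heel pain and tenderness "for at least three months without improvement will be considered for inclusion into the study". No upper limit on duration and no requirement about earlier treatment is given. The target is 50, described as a pilot.

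**Baseline data.** Under 7) Procedures, the information to be collected is "age, gender, height, weight, activity level, pain level, and physical exam findings including x-rays". Symptom duration and prior treatment are not in that list. Table 1 has, at visit -1 under standard of care, "focused history, x-rays, NSAIDs, heel cups"; the content of the history is not specified. The data abstraction sheet is an attachment that is not part of the public text.

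**Allocation.** Under Randomization and Blinding, assignment is 1:1 "by the application of an algorithm (e.g. even vs odd) to the number provided by a random-number generator". Blocks and strata are not mentioned. The clinical research coordinator and the ultrasound treatment team know the assignment.

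**Analysis.** The protocol's Statistical analysis paragraph names paired t-tests for the comparison between groups. The SAP's Statistical Calculations paragraph names t-tests of baseline against follow-up. Neither includes a covariate or a subgroup by duration.

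**The concern.** Both arms receive NSAIDs, heel cups and supervised physical therapy, with ITU or sham added. One subject may be starting such care for the first time; another may have had years of it without success. Both are eligible. If, as the background suggests, some patients settle on conservative care and others do not, this history plausibly affects how a subject does whatever the assigned arm.

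Three omissions then compound. Allocation does nothing to balance the factor, the listed baseline data do not include it, and the analysis does not use it. Any one of these would be easy to defend if the others were covered. Together, they mean that a reader of the finished trial could not tell from the listed data whether the arms were comparable in this respect, and the analyst could not adjust if they were not. Pilot status does not remove the point, because efficacy is the stated primary objective and differences are to be tested at P<0.05.

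**Working it through.** The documents give no derivation of the target of 50 (no effect size, SD or power), so there is no planned figure to reproduce. The check is how large a chance imbalance the stated allocation allows.

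**Inputs.** N = 50 (5) Study Population); each subject goes to either arm with probability 0.5, independently (a parity rule on a random number). The number K of long-standing subjects is not given. The background's 10% would mean K = 5, but that figure describes patients starting initial management. People already unimproved at three months may include more long-standing cases, so I show 10% to 50% as an assumed range.

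**Step 1: arm sizes.** With X ~ Binomial(50, 0.5), P(exactly 25:25) = C(50,25)/2^50 = 0.112, and P(30:20 or worse) = 2 × P(X ≤ 20) = 0.203. Unequal sizes alone matter little. At 30:20 the standard error rises by a factor √[(1/20 + 1/30)/(2/25)] = √(0.0833/0.0800) = 1.02.

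**Step 2: composition of the arms.** With a of the K long-standing and b of the 50 − K other subjects in arm 1, the difference in long-standing share is d = a/(a+b) − (K−a)/(50−a−b). I summed the probabilities Binomial(a; K, 0.5) × Binomial(b; 50−K, 0.5) over all pairs (a, b) meeting each threshold:

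| Assumed share (K) | P(arms differ by ≥10 points) | P(arms differ by ≥20 points) |
|---|---|---|
| 10% (5) | 0.27 | 0.02 |
| 20% (10) | 0.38 | 0.08 |
| 30% (15) | 0.44 | 0.14 |
| 40% (20) | 0.46 | 0.16 |
| 50% (25) | 0.48 | 0.20 |

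The mean of d is zero in every row.

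**Step 3: the 10% case in detail.** With K = 5, P(4:1 or 5:0) = 2 × (5 + 1)/32 = 0.375, and P(all five in one arm) = 2/32 = 0.0625. A 4:1 split with 25 per arm is 4/25 against 1/25, that is 16% against 4%, or 12 points.

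**Step 4: possible effect on the result.** The documents give no response rate by duration. If long-standing subjects responded 30 points less often (assumption), a 20-point imbalance would shift the arm difference by 0.20 × 0.30 = 0.06, or 6 points. For comparison, the standard error of a difference in proportions with 25 per arm at p = 0.5 is √(2 × 0.25/25) = 0.14, or 14 points.

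**Step 5: effect of the remedy.** With stratified blocks of 4, five long-standing subjects always split 3:2, so the 0.375 above becomes 0; ten split no worse than 6:4. Stratification does not make the subgroup informative. For an assumed 0.8 SD effect (noncentral t, two-sided 0.05), power is 10% with 3 v 2 subjects, 20% with 5 v 5 and 48% with 13 v 12.

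**The case against.** The case for leaving the plan alone is substantial, and much of it stands.

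- **The randomisation is sound.** A reader might take the parity rule for alternation, and so for a predictable or biased sequence. The text does not support that: the rule is applied to a random-number generator's output. The imbalance has mean zero and the type I error of a correct between-arm test already allows for it. Stratifying is a gain in efficiency and clarity, not the repair of an invalid method.
- **The likely effect is modest.** At the background's own 10%, a 20-point gap has probability 0.02. Even the 6-point shift in Step 4, which multiplies two assumed quantities, is well inside one standard error.
- **Duration may be recorded.** A reader might infer that it is not collected at all. That goes too far. Three months of symptoms is an entry criterion that staff must verify, a focused history is scheduled, the medical record is a data source, and the abstraction sheet is not public. What can be said is that it is not listed and has no planned use.
- **The refractory question is not an aim.** A reader might say that the trial fails one of its objectives. It does not: RPF appears as background rationale. The comparator is sham plus standard care, not surgery, so the trial was never designed to answer that question.

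It is also true that the background gives overall rates, not rates by duration or treatment history at enrolment. The factor is therefore plausible rather than proven. None of this answers the narrower point that the factor is left unbalanced, unlisted and unused at once.

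**Conclusion.** The point holds as a matter of precision and interpretability, not of bias. The plan admits a mix of durations and treatment histories, its own background suggests that this mix matters, and nothing in the allocation, listed baseline data or analysis deals with it. An imbalance of at least 10 points has a probability of roughly 0.27 to 0.48 over assumed shares of 10% to 50%; one of at least 20 points, 0.02 to 0.20. These figures rest on independent 1:1 allocation of exactly 50 subjects and on the assumed share, which the documents do not give. How far an imbalance would move the result is unknown.

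The documents do not support calling the allocation method faulty, saying that duration goes uncollected, or treating the refractory question as an unmet objective. The improvement is worth making because it is cheap and because treatment history missed at baseline is hard to recover reliably later.

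**What to change.** 1. **Record.** Add to the data abstraction list in 7) the months since symptom onset and yes/no items for prior NSAID, stretching or physical therapy, heel cup and injection. If the sheet already has them, say so in the protocol.
2. **Allocate.** Replace simple allocation with a computer-generated 1:1 list in randomly varying blocks, stratified by duration (<12 v ≥12 months, the background's own boundary). Conceal it from anyone who recruits or consents. The coordinator is a poor holder: 4) Resources includes that role among staff available to recruit and consent. The ultrasound treatment team, already unblinded, could hold it, provided its members do not recruit; 4) lists sonographers among the same staff, so this must be stated.
3. **Analyse.** Include the stratum as a covariate in a between-arm ITU-versus-sham model. The t-tests now named have no place for it, so the model must be written into both documents.
4. **Report.** Present results in subjects with ≥12 months of symptoms as descriptive only, and state that the trial is not designed to answer the refractory question.

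The cost is a few questions at a history already scheduled, a different list and one model term, with no extra visits or subjects. The downside is slightly more predictable allocation, which random block sizes and concealment limit.

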Diagnostic Ultrasound (Aim 2). Diagnostic ultrasound will be utilized to compare the changes in plantar fascia thickness that occurs over time in subjects treated with standard care to those treated with ITU plus standard of care. Diagnostic ultrasound imaging will be performed with an FDA approved ultrasound scanner (Spark® System, Ardent Sound, Inc. – Mesa, AZ, see Appendix 6 of proposal) using a coupling gel (Polysonic®, Parker Laboratories, Inc., Fairfield, NJ, see Appendix 7 of the attached proposal) by a trained sonographer or physician. The subject will be positioned prone on an exam table with the feet over the edge of the table. The plantar fascia of the affected and contralateral feet will be imaged. The width and depth of the fascia as well as the size and location of a hyperechoic lesion, when present, will be recorded using both long and short axis imaging. Change in plantar fascia thickness relative to the baseline measurement will be calculated. Decreased thickness of 0.8 mm or greater will be considered clinically significant as these changes have been shown to correlate with decreased pain and increased mobility.

Experimental Treatment: Intense Therapeutic Ultrasound (ITU). Subjects in the ITU group will receive standard treatment plus two treatments (at week 0 and week 2) of ITU to the affected plantar fascia (Table 1 in red). ITU treatment will be performed using a GEN II system (Guided Therapy Systems, Mesa, AZ). (Please see Appendix 5 of the Protocol.) We are seeking classification as a non-significant risk (NSR) device. (Please see the attached NSR statement.) Trained study personnel will conduct the treatments. The treatment session will last 15 – 20 minutes. During this time the subjects will be required to lay prone position on an exam table with their feet hanging over the end of the table. An average energy up to 5 joules / thermal zone will be administered to the symptomatic Plantar Fascia in a linear pattern along the Plantar Fascia (Figure 1) with up to 50 lines. Each line will include individual thermal zones, less than 1 mm³ in volume, centered at 10 – 13 mm depth, and approximately 2 mm apart.

[figure not shown]

Figure 1: The treatment site located around the insertion of the plantar fascia onto the posterior process of the calcaneus

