**FORM: Application for Human Research**

NUMBER	FORM DATE	PAGE
F200		15 of 18

presents no risk. Should subjects fail to comply with instructions given to them, they may be withdrawn from the study.

16) Sharing of results with subjects

The results of the study will not be shared with subjects.

17) Information management

N/A

18) Drugs, Devices, and Gases

Equipment for intense therapeutic ultrasound will be provided by [name] and [name] from Guided Therapy Systems and operated by trained sonographers.

- a) Name of drug/device: GEN II
- b) FDA approval status of the drug/device: We are seeking classification as a Non-Significant Risk (NSR) Device with the following reasons-
 - (a) GEN II will not be utilized nor is intended to be utilized as an implant. Additionally, the device does not present a potential for serious risk to the health, safety, or welfare of a subject.
 - (b) GEN II is not purported or represented to be for a use in supporting or sustaining human life and does not present a potential for serious risk to the health, safety, or welfare of a subject.
 - (c) The GEN II device is not of substantial importance in diagnosing, curing, mitigating, or treating disease, or otherwise preventing impairment of human health and does not present a potential for serious risk to the health, safety, or welfare of a subject.
 - (d) The GEN II does not otherwise present a potential for serious risk to the health, safety, or welfare of a subject.
- c) The GEN II will be controlled by the PI and/or representatives of the sponsor, Guided Therapy Systems:
 - i) The device will be stored in the PI's laboratory located in the Department of Orthopaedic Surgery, Biological Research Buildings, Building B Room 101 or in possession of GTS representatives.
 - ii) The site is sufficiently secure to protect the equipment.
 - iii) The storage condition for the equipment is not of concern beyond normal sheltered conditions.
 - iv) The GEN II device does not require stringent control and tracking of utilization.

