**FORM: Application for Human Research**

NUMBER	FORM DATE	PAGE
F200		16 of 18

- v) Trained sonographers will perform the ITU utilizing the GENII system.
- vi) Disposal issues are not relevant to the use of the GEN II system.

SECTION 4: LIST OF ATTACHMENTS FOR THIS SUBMISSION

Document Name	Version Date
1. F107 v030614	1. 3/6/14
2. [name] CV_Nov 2013	2. 11/2013
3. Ortho - Planters Fasciitis Broch_v7	3. 2/2014
4. Craig's List	4. 3/4/14
5. T502a - ICF Consent Form v031014	5. 3/10/14
6. T504a - PHI Authorization Form v031014	6. 3/10/14
7. T504b- PHI Autorizacion Spanish v031414	7. 3/14/14
8. map	8. 9/23/13
9. ITU protocol [name] final	9. 4/5/14
10. AE Log	10. 4/5/14
11. NSR Statement 022614	11. 2/26/14
12. ITU-PF patient Instructions	12. 3/10/14

Submission List for F200: Application for Human Research**Required items for all F200 submissions:**

- F107: Verification of Training Form
- Current PI/Co-PI CVs or biosketch, if not included with copy of grant application

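### The plan does not reserve the Aim 2 ultrasound scans and measurements for staff who are blinded to arm, so the unblinded treatment team may take them

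*Protocol*

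**What the plan says.** **Who knows the arm.** Protocol Section 3, item 7, Randomization and Blinding: "Only the clinical research coordinator and ultrasound treatment team will be privy to the subject's group assignment". The same paragraph says that the subject and most of the research team are blinded. It names no blinded outcome assessor.

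**Who treats.** The ITU paragraph of item 7 is general: "Trained study personnel will conduct the treatments". Item 18 (Drugs, Devices, and Gases) is more specific. The equipment comes "from Guided Therapy Systems and operated by trained sonographers", and sub-item v says: "Trained sonographers will perform the ITU utilizing the GENII system".

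**Who scans.** The Diagnostic Ultrasound (Aim 2) paragraph allows imaging "by a trained sonographer or physician". It sets no blinding condition on that person or on whoever makes the measurements.

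**Who is available.** Item 4 (Resources): "Personnel available to conduct the study include 2 surgeons, 1 clinical research coordinator, 2 sonographers, 1 medical student, and 2 undergraduate assistants". The list does not say which of them treat and which scan.

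**When.** Table 1 places randomization at time -1. Diagnostic and treatment ultrasound fall at the same visits at weeks 0 and 2, and diagnostic ultrasound alone at weeks 4, 6 and 12.

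**The SAP.** It describes how lesion volume is calculated from three measured radii, but it names no reader and no masked review.

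**The concern.** The role that delivers treatment, and so knows the assignment, is one of the two roles allowed to take the outcome scans. Nothing visible keeps the two jobs apart.

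The Protocol intends to compare thickness and lesion findings between the arms (Lay Summary; item 7, Statistical analysis covers thickness). These measurements depend on probe position and on where the calipers are placed. A measurer who expects the ITU foot to improve can shift readings in one direction, by a different amount in each arm. An analysis of the recorded values cannot separate that shift from a treatment effect.

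Randomization comes before week 0, so even the baseline scan, from which change is calculated, may be taken by someone who knows the arm. The trial uses a sham to blind subjects, and an unblinded measurer would weaken that protection for the imaging outcomes.

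The Aim 1 outcomes are reported by subjects who are stated to be blinded, so they are not directly affected.

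**Working it through.** **Step 1. Could an unblinded person take the scans?**

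| Question | Answer in the Protocol | Place |
|---|---|---|
| Who knows the arm? | Coordinator and the ultrasound treatment team as a whole | Item 7, Randomization and Blinding |
| Who delivers ITU? | Trained sonographers | Item 18, opening and sub-item v |
| Who may scan for Aim 2? | A trained sonographer or a physician | Item 7, Diagnostic Ultrasound |
| How many sonographers? | Two, duties not divided | Item 4 |
| Is a blinded scanner or reader required? | No visible sentence | – |

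The first three rows overlap in one role, the sonographer. The fourth row does not remove the overlap, and the fifth shows no rule that would. The text therefore permits arm-aware measurement, although it does not say that this occurs.

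**Step 2. How large could the effect be?** The documents give no figure to reproduce, so this is an illustration for the Protocol's between-group thickness comparison.

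Inputs from the Protocol:
- Target of 50 subjects (item 5), randomized 1:1 (item 7), so 25 per arm.
- Significance level 0.05 (item 7, Statistical analysis).
- Clinically significant thickness decrease of 0.8 mm (item 7, Diagnostic Ultrasound).

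Assumptions, because the documents give none:
- Between-arm reading bias b of 0.1, 0.2 or 0.4 mm. These are 0.1/0.8 = 12.5%, 0.2/0.8 = 25% and 0.4/0.8 = 50% of the 0.8 mm threshold.
- SD s of thickness change of 0.8 to 1.5 mm.
- No true effect and a two-sided test.
- An unpaired t-test on change. The Protocol names paired t-tests, but a comparison of two independent arms needs an unpaired one.

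Formula: noncentrality = b / (s × √(2/25)), with df = 48. The false-positive rate is the two-sided rejection probability under the noncentral t distribution.

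Worked case: b = 0.2 and s = 0.8 give 0.2 / (0.8 × 0.2828) = 0.884, and a rejection rate of 0.139.

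| Bias b | s = 0.8 mm | s = 1.0 mm | s = 1.5 mm |
|---|---|---|---|
| 0.1 mm | 0.072 | 0.064 | 0.056 |
| 0.2 mm | 0.139 | 0.107 | 0.075 |
| 0.4 mm | 0.410 | 0.283 | 0.152 |

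A simulation of 200,000 trials at b = 0.2 mm gave 0.139 (s = 0.8) and 0.074 (s = 1.5). With 20 per arm, b = 0.2 mm gives 0.120 (s = 0.8) and 0.070 (s = 1.5).

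**The case against.** Four arguments weigh against the concern.

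1. **The blinding rule is restrictive.** Anyone outside the coordinator and the treatment team is blinded by default. A physician, or a sonographer who does not treat, meets the rule as written. The treatment team is not defined by name, and item 18 adds: "The GEN II will be controlled by the PI and/or representatives of the sponsor, Guided Therapy Systems". That phrase introduces storage and security items, however, and sub-item v of the same list still names sonographers as those who treat. The argument shows that unblinded scanning is not certain. It does not show that it is prevented.

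2. **The document reviewed is an ethics application.** It refers throughout to a separate protocol and its appendices, listed in Section 4, which are not available here. Scanner and reader rules could well be there. This limits confidence. If such a rule exists, citing it in the application is enough.

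3. **The numbers rest on assumptions.** Both the bias and the SD are assumed. The test illustrated differs from the paired test named in the Protocol. The SAP has no thickness analysis, and its t-tests compare follow-up with baseline. All of this stands. The figures show only what a given bias would do, and nothing is quantified for lesion volume, the one imaging outcome that the SAP keeps. The gap in the text does not depend on the figures.

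4. **Aim 2 is not the primary outcome, and this is a pilot of 50.** This limits the consequence. It does not remove the need for unbiased measurement of the only efficacy outcomes that subjects do not report themselves.

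**Conclusion.** The concern holds. The visible plan permits members of an unblinded treatment team to take and measure the Aim 2 scans, and no visible sentence requires otherwise. Whether they do so is not stated.

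The scope is fascia thickness and lesion findings. The Protocol calls the lesion hyperechoic and the SAP calls it hypoechoic, but the point applies to either.

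Over the assumed range, the false-positive rate of the thickness comparison rises from 0.05 to between 0.056 (bias 0.1 mm, SD 1.5 mm) and 0.410 (bias 0.4 mm, SD 0.8 mm). Bias and SD are assumptions throughout.

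The change should be made. Confidence is medium, because the attached protocol could not be read.

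**What to change.** **In the Protocol.** State in Randomization and Blinding and in Diagnostic Ultrasound (Aim 2) that scans are taken and measured only by existing staff who are not privy to any subject's assignment. That means a blinded physician, or a sonographer kept outside the treatment team with no access to assignments. It is not enough to bar the person who treated that subject, because the whole team is unblinded.

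**Where images are stored.** Have a blinded team member measure thickness and lesion radii from images coded to hide arm and visit. Someone else should hold the key that re-links each subject's images.

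**If scanning is complete.** The SAP is written in the past tense, so this may be the case. Re-read the stored images blind. This addresses bias in the measurement, though not bias from how the probe was held. If no usable images exist, report who measured and whether they knew the arm.

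**Cost.** The text change is short and needs no new staff. Scheduling becomes less flexible, since one of the two sonographers stays off the treatment team or a blinded physician scans. Coding and re-linking take time. A blind re-read is possible only if images were kept in measurable form, which the documents do not state.
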